HEALTHY MIND© VR (Paris, France): a 15-minute VR therapeutic session immersing the patient in an artificial world created from computer-generated images using software connected to the PICO 4E headset. The patient can choose one of several types of environments (beach, mountains, lake and others) using synthetic animated images, breathing exercises and advanced psychological/relaxation principles such as cardiac coherence or hypnotic verbal accompaniment.

Variables will be reported in a standardized way in the CRF in the following order:

- Before intravenous cannulation
 - Patient identification number
 - Patient demographics (gender and age)
 - Inclusion and exclusion criteria
 - Patient's VAS for pain intensity
 - Patient's VAS for anxiety
 - Patient's VAS for fatigue
 - Patient's VAS for cramps and heart rate measurement
- After intravenous cannulation:
 - Characteristics of intravenous cannulation. Specificity.
 - Patient's VAS for pain intensity
 - Patient's VAS for anxiety
 - Patient's VAS for fatigue
 - Patient's VAS for cramps and heart rate measurement
 - Patient's VAS for comfort and acceptability of VR headset use

Data collection

	Pre inclusion V0 (*)	Visite 1		Visite 2		Visite 3	
		Before	Post	Before	Post	Before	Post
Screenning and information	✓						
Consent form signed	✓						
Demographic Data ¹		✓					
Physiological data ²		✓	✓	✓	✓	✓	✓
VAS ³ Anxiety, Pain and Fatigue		✓	✓	✓	✓	✓	✓
HAD scale		✓			✓		✓
Patient/Family Satisfaction			✓		✓		
Professional Satisfaction							✓

Expected Outcomes

Primary outcomes: Evaluated by the Visual Analogue Scale (VAS)

- Evaluate the impact of VR-induced 3D immersion on anxiety during cannulations through visualization of Healthy Mind VR therapeutic sessions (using a PICO 4E VR headset). Comparison of patients' anxiety levels before and after the procedure with and without VR. Assessed by visual analog scale (VAS).
- Evaluate the impact of VR-induced 3D immersion pain during cannulations through visualization of Healthy Mind VR therapeutic sessions (using a PICO 4E VR headset). Comparison of patients' pain levels before and after the procedure with and without VR.

Secondary outcomes: Evaluated by the Visual Analogue Scale (VAS)

- Evaluation of fatigue levels after the procedure for patients with and without VR.

- Examine factors associated with boredom and weariness with and without VR.
- Evaluation of patient satisfaction with and without VR.

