- Assessment of healthcare professionals' satisfaction levels during and after the procedure with and without VR.
- Assessment of family members' satisfaction levels during and after the procedure with and without VR.
- Assessment of other outcomes of interest (exploratory)
 - Evaluation of the heart rate with and without VR (cardiac frequency)

Sample size calculation:

Due to the exploratory nature of the study, the sample size was calculated on the basis of the number of possible orders of relaxation sessions, which was calculated as follows: 3 types of options x 3 x 2 = 18 possible session orders.

At least two different patients had to be enrolled for each type of option (i.e. 36 patients), to ensure a homogeneous distribution of the different possible orders of relaxation within the study population. 100 patients had to be enrolled in the study, to take account of patients lost to follow-up and missing data. Study power was set at 80% to demonstrate a clinically significant difference greater than 2, with an alpha threshold of 0.05.

Statistical analysis of primary objectives:

The difference between two sessions (VR vs SOC) will be followed by a comparison of the proportions of patients who achieved at least a 25% improvement in anxiety, pain, fatigue, and depression, assessed by the VAS and HAD scale in post-cannulation procedure. The value provided to patients in the VR session during intravenous cannulation procedure and patients with SOC, will be compared using Student's t-test, after verification of the homoscedasticity hypothesis by a Levene's test.

If this hypothesis is not verified, the Mann-Whitney test will be performed, for which the number of patients required to maintain 90% power is 35 per group. If the reduction is not 25% but only 20%, with a power of 80%, this difference will be highlighted.

A 2-factor repeated-measures ANOVA model (VR vs. non-VR session and time before vs. time after) will be developed. Another statistical model will be developed, in order to see the time and session effect and to see if there is an interaction between the 2 factors. Finally, the correlation between basal anxiety scores on the different VAS, HAD scales will be estimated using Pearson's or Spearman's coefficients; the same statistical approach will be used to assess correlations between basal anxiety and their levels measured after the cycles by the VAS.

Statistical analysis of secondary objectives:

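### The named VR-versus-SOC test does not use the same-visit pre-cannulation VAS, and the planned model that does use it is not designated primary

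*Combined protocol and SAP*

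**What the plan says.** Expected Outcomes defines both primary outcomes, anxiety and pain, as comparisons of "levels before and after the procedure with and without VR". The Data collection table schedules VAS anxiety, pain and fatigue before and after cannulation at visits 1, 2 and 3, and none during the procedure. Fatigue is a secondary outcome defined on the post level alone: "Evaluation of fatigue levels after the procedure for patients with and without VR".

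Statistical analysis of primary objectives then lists three things:

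- A comparison of the proportions improving by at least 25%, "assessed by the VAS and HAD scale in post-cannulation procedure". The reference value for improvement is not stated.
- A between-session test: "The value provided to patients in the VR session during intravenous cannulation procedure and patients with SOC, will be compared" by Student's t-test. If the equal-variance check fails, "the Mann-Whitney test will be performed, for which the number of patients required to maintain 90% power is 35 per group".
- "A 2-factor repeated-measures ANOVA model (VR vs. non-VR session and time before vs. time after) will be developed", and a further model "to see the time and session effect and to see if there is an interaction between the 2 factors".

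None of these is named as the primary test. Under Interventions, every patient has SOC at visit 1 and VR at visits 2 and 3. Limitations confirms that the order was deliberately not randomised.

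**The concern.** The between-session test names no pre value, change score or covariate. If it is run on post-cannulation scores, a patient's state on arrival that day stays in the comparison.

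In a randomised crossover that would mostly be noise. Here the order is fixed, so arrival differences can be systematic: patients may come to visits 2 and 3 more used to the study, or calmer because they expect VR. A post-only contrast counts any such difference that lasts through the procedure as a VR benefit. The measurement that would reduce this is already scheduled at every visit.

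**Working it through.** **What the plan's figures allow.** The 36 patients reproduce (3 x 3 x 2 = 18 orders, two patients each). The documents give no SD, correlation or dropout rate, so neither the 100 nor the 35 per group can be derived. If the stated difference of 2 means VAS points, 35 per group at 90% power fits an SD of about 2.5: n = 2(1.960 + 1.282)^2 x 2.5^2 / 2^2 = 32.8, so 33, and 33 / 0.955 = 34.6, so 35 for Mann-Whitney. I use SD 2.5 below as an assumption.

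**What the planned ANOVA does.** Let D_pre and D_post be a patient's VR-minus-SOC differences before and after cannulation.

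- Session-by-time interaction: tests the mean of D_post - D_pre, the paired comparison of within-visit change. In simulated data for 100 patients, the interaction F was 35.622 and the squared paired t on change was 35.622. This part of the plan therefore uses the pre value.
- Session main effect: tests the mean of (D_pre + D_post)/2. A 1-point fall at both times gives (-1 - 1)/2 = -1, carried in full. A true VR effect d on the post score alone gives d/2, so it is halved.

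**Three candidate estimators.** Assumptions: equal SD of 2.5 at all time points; correlation 0.5 between visits at the same time point; pre-post correlation within a visit w = 0.6/0.7/0.85 (weak case 0.3); pre-post correlation across visits c = 0.4/0.4/0.45 (weak case 0.2).

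- Slope of D_post on D_pre = (w - c)/(1 - 0.5) = 0.4/0.6/0.8 (weak 0.2). With equal variances this is also their correlation r.
- Variance relative to paired post-only: adjusted 1 - r^2; change score 2(1 - r).
- Drift A, no VR effect, level 1 point lower both before and after at the VR visit: post-only -1; adjusted -1 + r; change score 0.
- Drift B, no VR effect, level 1 point lower on arrival, of which only the fraction r remains afterwards: post-only -r; adjusted 0; change score 1 - r.

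| r | Variance, adjusted | Variance, change | Drift A: post-only / adjusted / change | Drift B: post-only / adjusted / change |
|---|---|---|---|---|
| 0.2 | 0.96 | 1.60 | -1.0 / -0.8 / 0 | -0.2 / 0 / +0.8 |
| 0.4 | 0.84 | 1.20 | -1.0 / -0.6 / 0 | -0.4 / 0 / +0.6 |
| 0.6 | 0.64 | 0.80 | -1.0 / -0.4 / 0 | -0.6 / 0 / +0.4 |
| 0.8 | 0.36 | 0.40 | -1.0 / -0.2 / 0 | -0.8 / 0 / +0.2 |

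The change score is noisier than post-only when r is below 0.5.

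**Cost of adjusting when the mean pre difference is not zero.** The SD of D_pre is 2.5 x sqrt(2 x 0.5) = 2.5. A mean pre difference of 1 point multiplies the variance of the adjusted estimate by 1 + 1^2/2.5^2 = 1.16. The relative variances become 1.16 x 0.84 = 0.97, 1.16 x 0.64 = 0.74 and 1.16 x 0.36 = 0.42. In the weak case, 1.16 x 0.96 = 1.11, slightly worse than post-only.

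**Scale.** With 100 patients, the paired post-only SE is 2.5 x sqrt(2 x 0.5/100) = 0.25. If the test is run as written, with two independent groups of 100, it is 2.5 x sqrt(2/100) = 0.354.

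**The case against.** A reader might infer that the plan ignores the pre-cannulation VAS altogether. The documents do not support that: the same section plans the session-by-time ANOVA, and its interaction is exactly the comparison of within-visit change. A reader might also take the t-test to be explicitly post-only. It is not. The word post-cannulation belongs to the preceding sentence, on 25% improvement. The post value is the natural reading because no VAS is scheduled during the procedure, but it remains a reading.

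Three further objections carry weight:

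- **Bias.** Under a drift equal before and after, the planned interaction gives 0, while the adjusted contrast still leaves -0.6/-0.4/-0.2. This stands, and it is why the change score must be reported too. But the change score is right only if the arrival difference persists unchanged. If it partly fades (drift B), the change score errs the other way.
- **Power.** The variance figures use a paired SE, whereas the named tests are two-group tests. If the planned difference of 2 means VAS points, it is 2/0.25 = 8 standard errors, so power is not at stake. The case rests on attribution and interval width.
- **Fatigue.** It is a secondary outcome that may legitimately be defined on the post level. Aligning it is for consistency, since the primary-analysis section also lists fatigue.

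The ANOVA does not settle the matter. It is not designated primary, no contrast or decision rule is given, and its session main effect carries a common drift in full.

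**Conclusion.** The concern holds in this limited form. The named VR-SOC test leaves out a same-visit baseline that the trial collects. The model that includes it has no stated priority, and nothing uses the pre value as a covariate. With SOC fixed at visit 1, a persistent 1-point drift with no VR effect would read as a full 1-point benefit in a post-only contrast or in the ANOVA session main effect. Adjustment would cut that to 0.6/0.4/0.2 points and leave 84%/64%/36% of the paired post-only variance at r = 0.4/0.6/0.8.

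These sizes rest on an assumed SD of 2.5 and assumed correlations. At r = 0.2 the gain is 4% of variance, and it becomes a small loss if the mean pre difference is 1 point. It would also be wrong to infer that adjustment cures the fixed order: it reduces bias from arrival level and does nothing about order effects that arise during the procedure. The change should be made, but the plan is not without any use of the pre value.

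**What to change.** Replace the t-test/Mann-Whitney comparison of the value with one pre-specified within-patient contrast for pain and for anxiety, and treat fatigue in the same way:

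- Regress each patient's post difference (VR visit minus visit 1) on the same patient's pre difference. Report the intercept as the VR effect, with its 95% CI.
- State whether visit 2, visit 3 or their mean supplies the VR value.
- Report the session-by-time interaction (the change-score difference) and the unadjusted post difference beside it. If the three disagree, the result depends on how arrival differences carry over.
- Define the pre-cannulation VAS as the one taken before the headset starts. Interventions has VR starting 5 minutes before cannulation and does not say whether the VAS comes first; if it comes later, the pre value may already contain a VR effect.

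No new CRF item is needed. The cost is analysis wording, plus possibly a clarified time for the pre-cannulation questionnaire. The adjusted figure excludes any calming that comes from expecting VR, which is one reason to show the unadjusted figure too. With weak correlation and a non-zero mean pre difference, its interval can be slightly wider than the unadjusted one.

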- Patient of legal age but subject to legal protection measure or unable to express their consent
- Patient suffering from uncontrolled epilepsy
- Patient with visual or auditory disorders
- Patient suffering from claustrophobia or motion sickness
- Patient with face infection
- Patient with dissociative psychiatric pathologies and autism

After consulting the patients' medical records, and checking that there are no exclusion criteria, the investigators will introduce themselves to the patients and their families, informing them that they are eligible and offering them to take part in the study.

[figure not shown]
Patients will be informed that the study aims to investigate the immersive effect of VR during intravenous cannulation procedure, and they will be provided with a patient information sheet and flyer.

If the patient agrees in principle to take part in the study, and after obtaining informed, signed, written consent, each patient will be given a personalized schedule of the various management appointments and the questionnaires used as part of the protocol.

Interventions:

Patients will benefit from the standard of care for their first visit, then they will have a VR session on their second visit, then another session in VR for their third visit. The VR session starts 5 minutes before the intravenous cannulation procedure, 10 minutes during the procedure and 5 minutes after, for a total of 20 minutes. Before and after the intravenous cannulation procedure, the investigator will complete the Case Report Form for data collection from patients.

All participants will complete questionnaires before and after the procedure at visit 1 (V1), V2 and V3. The interval between visits is 3 weeks, in line with clinical practice at the referral centre.

The two options for managing anxiety and general symptoms are:

1) Standards of care (SOC) :

Thalassemia patients require lifelong monthly blood transfusions to survive. During routine visits, an experienced healthcare provider inserts intravenous cannulation under aseptic technique. Children are escorted by parents to offer support and distraction. This short procedure is accompanied by pain and anxiety for all the involved parties.

2) Virtual reality (VR)

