The difference between two sessions (VR vs SOC) will be followed by a comparison of the proportions of patients who achieved at least a 25% improvement in satisfaction, assessed by the VAS. Comparison will be carried out using the same method used for primary objectives.

Risk factors associated with dissatisfaction will be explored using uni and multivariate logistic regression models.

Overall ethical considerations

This study is useful both for its scientific contribution and for improving the comfort of thalassemia patients undergoing invasive procedures such as intravenous cannulation. Through this study, we will gain insight into the impact of virtual reality as an adjuvant to care for intravenous cannulations.

Our research will be conducted in accordance with the Declaration of Helsinki and the National Act on Research Involving Human Subjects. We will ensure that no coercion or pressure to participate is exerted on patient-participants. Written informed consent will be obtained from each participant. At any time and without explanation, participants may leave the study without any effect on future care, treatment or working conditions.

With the exception of necessary personal data (socio-demographic information), members of the research team will maintain confidentiality with patient information. Participant data will be anonymised or coded as appropriate and stored securely.

Limitations

A limitation of our study is that randomising the order of intervention sessions was not favourable for our investigation. Because our participants all suffer from chronic disease, the most appropriate way to get a baseline for pain and anxiety perception is before exposure to VR intervention. If done in an alternative manner, i.e. starting with a VR session and then not having VR, it would be more likely for patients to over-report their feelings of pain or anxiety, thus skewing the results. Hence, ordering the sessions in the way that was ultimately decided was, we believe, in favour of reducing bias.

The results of this study will be applicable to all population groups which do not fall under our exclusion criteria (as mentioned in the methods).

Project Timeline

	Feb 2024	Mar 2024	15th April – 15th June	July 2024	Aug 2024	Nov-Dec 2024
IRB Submission						
Site preparation, staff training						
Screening and inclusion						
Data management						
Statistical analysis						
Dissertation writing						

Acknowledgements

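### VR versus SOC is a within-patient comparison, but the named tests are for independent groups and none of the planned analyses is named as decisive

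*Combined protocol and SAP*

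**What the plan says.** All references are to the combined protocol and SAP.

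- **Interventions:** "Patients will benefit from the standard of care for their first visit, then they will have a VR session on their second visit". The third visit is again VR. All participants are assessed before and after the procedure at all three visits.
- **Statistical analysis of primary objectives, group tests:** VR and SOC values are compared by Student's t-test, "after verification of the homoscedasticity hypothesis by a Levene" test. If equal variances are not supported, "the Mann-Whitney test will be performed, for which the number of patients required to maintain 90% power is 35 per group".
- **Same section, models:** "A 2-factor repeated-measures ANOVA model (VR vs. non-VR session and time before vs. time after) will be developed". Then: "Another statistical model will be developed, in order to see the time and session effect and to see if there is an interaction". Neither is ranked against the t-test.
- **Same section, responders:** the proportions compared are those with at least "a 25% improvement in anxiety, pain, fatigue, and depression, assessed by the VAS and HAD scale in post-cannulation procedure". No test is named for these proportions.
- **Sample size calculation:** 100 patients, with 80% power to "demonstrate a clinically significant difference greater than 2, with an alpha threshold of 0.05". No SD or within-patient correlation is given.
- **Statistical analysis of secondary objectives:** "Comparison will be carried out using the same method used for primary objectives".

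**The concern.** Student's t-test alone could mean the paired version. Levene's test, Mann-Whitney and a per-group sample size together point to two independent samples. No paired t-test, Wilcoxon signed-rank test or McNemar test is named anywhere.

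Applied to two measurements on the same patient, an independent-samples test uses the wrong standard error, so its p-values and confidence intervals are wrong. Levene's test does not help: equal variance of two columns is not the assumption that matters for a paired difference.

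The second problem is the lack of a hierarchy. The plan contains unpaired tests, a repeated-measures ANOVA and a further unspecified model. For moderate effects these can disagree, and nothing written in advance says which one decides. The VR value could come from visit 2, visit 3, or both.

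**Working it through.** **Inputs.** From the documents: 100 patients, alpha 0.05 (taken as two-sided), difference 2, 35 per group at 90% power. Assumed, because the documents give none: SD per visit *s*, correlation ρ between a patient's SOC and VR values, and the smaller difference of 1.

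**1. The plan's own figure.** The 35 cannot be reproduced without an SD. Back-solving with n per group = 2(1.960 + 1.282)²s²/δ², times π/3 for Mann-Whitney, and δ = 2:

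- s = 2.0 gives 24 per group by Mann-Whitney, s = 2.5 gives 35, and s = 3.0 gives 51.
- Exactly 35 needs s of about 2.52 (Mann-Whitney) or 2.58 (t-test).

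So 35 fits an independent-groups calculation at an unstated SD near 2.5 to 2.6. This joins figures that the text does not join: the difference of 2 is tied to 80% power, and the 35 to 90%.

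**2. Type I error and interval width, one VR value per patient.** The SE assumed by the unpaired test is s√(2/n). The true SE is s√(2(1−ρ)/n). Hence type I error = 2[1 − Φ(1.96/√(1−ρ))], and intervals are too wide by 1/√(1−ρ).

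| ρ | Type I error | Interval width ratio |
|---|---|---|
| 0.1 | 3.9% | 1.05 |
| 0.3 | 1.9% | 1.20 |
| 0.5 | 0.56% | 1.41 |
| 0.7 | 0.03% | 1.83 |

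Example at ρ = 0.5: 1.96/√0.5 = 2.77, and 2[1 − Φ(2.77)] = 0.0056.

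**3. Power for the same contrast.** Unpaired power = Φ((δ − 1.96·SE_assumed)/SE_true). Paired power = Φ(δ/SE_true − 1.96).

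- n = 100, δ = 1, s = 3, ρ = 0.5: SE_assumed = 3√0.02 = 0.424 and SE_true = 3√0.01 = 0.300. Unpaired: Φ((1 − 0.832)/0.300) = Φ(0.56) = 71%. Paired: Φ(3.33 − 1.96) = Φ(1.37) = 92%. In simulation (20,000 runs), 20% of trials were significant by the paired test only.
- n = 100, δ = 2, s = 2.58: both are about 100% at every ρ above.

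**4. The session-by-time interaction is a different contrast.** Take the mean before-to-after change at visits 2 and 3 minus the change at visit 1, and assume that all six measurements share correlation ρ. One change has variance 2s²(1−ρ), and the mean of two has s²(1−ρ). The contrast therefore has variance 3s²(1−ρ)/n, against 2s²(1−ρ)/n in step 3. At n = 100, δ = 1, s = 2.58:

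| ρ | Unpaired | Paired, same contrast | Interaction |
|---|---|---|---|
| 0.1 | 79.5% | 82.4% | 65.5% |
| 0.3 | 82.5% | 90.6% | 76.3% |
| 0.5 | 86.5% | 97.2% | 88.6% |
| 0.7 | 92.3% | 99.9% | 98.3% |

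**5. Restating 35 as a total.** For a paired t-test with 35 patients, δ = 2 and 90% power, the SD of the within-patient difference may be up to 3.55.

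**The case against.** The strongest reply is that the study calls itself exploratory, already plans a repeated-measures ANOVA, and would reach the same conclusion with either test at a difference of 2 and 100 patients. All of that stands, and it limits the seriousness of the point. It does not make the named tests right or say which analysis decides.

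Four stronger readings are tempting, and the documents do not support them:

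- **That the plan ignores the pairing.** It does not, because the repeated-measures ANOVA can respect it. What is missing is its rank.
- **That false positives are inflated.** With one VR value and positive correlation the error goes the other way. Inflation would need visits 2 and 3 entered as independent records, which the plan does not state. It would also need the correlation between those visits to exceed 4 times that between visit 1 and the VR visits, which is impossible once the latter reaches 0.25.
- **That any within-patient analysis gains power.** Step 4 shows the interaction below the unpaired test at ρ of 0.1 and 0.3 under equal correlations. A higher within-visit correlation would help it. The gain in step 3 belongs only to the paired test of the same contrast.
- **That the plan assumes an SD of about 2.6.** That value is only back-solved from figures given separately.

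The Data collection table has no HAD value after the SOC procedure and no professional satisfaction value without VR. That is a separate schedule issue, not a consequence of unpaired testing.

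**Conclusion.** The point holds and should be fixed. The design is within-patient, the named tests are for independent samples, the secondary outcomes inherit them, and no analysis is decisive. The consequence is lost precision and an open choice between analyses, not spurious significance. Under the assumed correlations of 0.1 to 0.7, type I error falls to between 3.9% and 0.03%, and intervals are 5% to 83% too wide. The loss matters for effects smaller than 2 or for larger SDs. At a difference of 2, an SD near 2.6 and 100 patients it does not change the conclusion. All sizes rest on assumed SDs and correlations and on equal variance across visits.

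**What to change.** 1. Replace the t-test, Levene and Mann-Whitney sequence with a paired t-test on the within-patient VR-minus-SOC difference, with Wilcoxon signed-rank as the non-parametric check. Any supportive t-test must also be paired.
2. State one rule for visits 2 and 3, for example their mean, and use it wherever both visits are measured.
3. Name one within-patient analysis as primary for anxiety VAS and pain VAS. It may be the paired contrast of post-procedure values or the session-by-time interaction of the planned model. These are different estimands, so the choice should be made on the question asked, with power worked out for the one chosen.
4. Delete the 35 per group, or restate it as a total number of patients with the assumed SD of the within-patient difference (about 3.5 for 90% power at a difference of 2).
5. Say what the 25% improvement is measured against. If it is defined within each visit, compare the proportions by McNemar's test.
6. In the secondary analysis, compare patient/family satisfaction after visit 1 and after visit 2 by a paired test. The schedule collects it only then, so visit 2 supplies the VR value.
7. State that pairing does not remove the confounding of VR with visit order.

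The cost is wording plus one decision on the estimand. No new data or patients are needed.

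### The planned 25% responder comparison for satisfaction has no standard-care proportion, because patients and families are rated only after the procedure at Visits 1 and 2

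*Combined protocol and SAP*

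**What the plan says.** The section on statistical analysis of secondary objectives starts from the difference between the VR and SOC sessions. It then adds a comparison of "the proportions of patients who achieved at least a 25% improvement in satisfaction, assessed by the VAS". On method it says only: "Comparison will be carried out using the same method used for primary objectives".

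The primary-objectives section supplies that method: Student's t-test after a Levene test, with Mann-Whitney as the fallback, and a two-factor repeated-measures ANOVA with session (VR or not) and time (before or after) as factors.

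The objective under Secondary outcomes is worded as a level, not a change: "Evaluation of patient satisfaction with and without VR". Satisfaction of family members and of professionals is also promised with and without VR.

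The order of sessions is fixed under Interventions: "Patients will benefit from the standard of care for their first visit, then they will have a VR session on their second visit". Visit 3 is again VR.

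In the Data collection table the row "Patient/Family Satisfaction" has two ticks, Visit 1 Post and Visit 2 Post. The row "Professional Satisfaction" has one, Visit 3 Post.

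**The concern.** A comparison of two responder proportions needs an improvement for each patient under each condition, and each improvement needs a reference value. The 25% rule suits pain, anxiety and fatigue, which are rated before and after every procedure. It has been carried over to an outcome that is collected differently, and the plan names no reference value for it.

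If this stays as written, the analyst will have to choose a satisfaction endpoint after the data are in: which visit is the reference, what counts as improvement, and which test to use. That choice would not be pre-specified. The tests named for the comparison also ignore that both ratings come from the same person.

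**Working it through.** The check is a reading of the schedule. The plan gives no sample size, power or alpha figure for satisfaction, so there is no figure to reproduce.

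**Step 1. Ticks in the Data collection table, read by column**

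| Item | V1 Before | V1 Post | V2 Before | V2 Post | V3 Before | V3 Post |
|---|---|---|---|---|---|---|
| VAS anxiety, pain, fatigue | yes | yes | yes | yes | yes | yes |
| HAD | yes | – | – | yes | – | yes |
| Patient/family satisfaction | – | yes | – | yes | – | – |
| Professional satisfaction | – | – | – | – | – | yes |

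The row for "Anxiety, Pain and Fatigue" fills all six columns, and the HAD row has its own distinct pattern. The columns therefore appear to be intact, and the gaps in the satisfaction rows look intended.

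**Step 2. Improvement within a visit.** This needs a Before and a Post rating at the same visit.
- Anxiety, pain and fatigue: available at 3 of 3 visits.
- Patient/family satisfaction: available at 0 of 3 visits, so for neither SOC (V1) nor VR (V2, V3).

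**Step 3. Improvement between visits.** Let S1 be the V1 Post rating and S2 the V2 Post rating. The only change that can be formed is (S2 − S1)/S1, and the responder rule would be (S2 − S1)/S1 ≥ 0.25. This gives one proportion for the whole cohort, describing VR relative to SOC. An SOC proportion would need a rating earlier than V1 Post, and none is scheduled. A single proportion could be tested against a stated reference value, but the plan states none.

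**Step 4. What can be compared.** S1 and S2 exist for the same people, so the difference in level, S2 − S1, can be estimated for patients and for families. This is what the stated objective asks for.

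**Step 5. Whether the borrowed tests fit S2 − S1.** Suppose for illustration that both ratings have standard deviation s, with within-person correlation r and n patients. Neither s nor r is given in the plan.
- Variance used by an independent-groups t-test: 2s²/n.
- Correct variance for paired ratings: 2s²(1 − r)/n.

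The two agree only if r = 0. With positive r, the independent-groups test overstates the standard error by a factor of 1/√(1 − r). Mann-Whitney makes the same independence assumption. The repeated-measures ANOVA does respect pairing, but its time factor needs the Before rating that Step 2 shows is absent.

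**Step 6. Professionals.** Their only rating is at V3, a VR visit. With no SOC rating, neither a change nor a difference in level can be formed.

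**Step 7. CRF list.** The CRF variables under Interventions include no satisfaction VAS. The nearest entry, "Patient's VAS for comfort and acceptability of VR headset use", is specific to the headset and cannot apply to the SOC visit.

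**The case against.** The strongest reply is that the plan has two steps, and the first, the difference between VR and SOC sessions, can be run on post-procedure levels. That stands. A reader might infer that satisfaction cannot be analysed at all; the documents do not support this for patients and families. Only the responder step is undefined.

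Second, other text could be read as supplying a Before rating. Interventions says in general terms that participants fill in questionnaires before and after the procedure at all three visits. The opening summary speaks of provider and family satisfaction pre and post VR. Secondary outcomes refers to family and professional satisfaction during and after the procedure. None of these establishes a pre-procedure rating of patient satisfaction. The first names no instrument; the second at best contrasts the SOC visit with a VR visit; the third adds a time point with no column in the schedule. The item-level schedule is more specific than all three. Its footnotes and the appendix content are not in the text available, which is a minor caveat.

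Third, the plan is not purely unpaired, because it includes a repeated-measures ANOVA. That is right, but the model as specified does not fit an outcome rated only after the procedure.

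Fourth, a reader might add a ceiling argument. On an assumed 0–10 scale with higher meaning better, a 25% gain requires 1.25x ≤ 10, so x ≤ 8, and anyone above 8 at Visit 1 could not respond. The arithmetic is right, but it criticises a Visit 1 to Visit 2 responder rule that the plan does not state. No satisfaction distribution is given either, so the number affected is unknown. The point does not rest on it.

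Finally, satisfaction is a secondary outcome and the sample-size section calls the study exploratory. No primary conclusion depends on this, which limits the weight of the point but does not remove it.

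**Conclusion.** The point holds in a limited form. The comparison of VR and SOC on the share with a 25% improvement in satisfaction is wrong as written. The SOC proportion is undefined for every patient in the planned cohort of around 100, and the only change that can be formed gives one proportion without a comparator. The comparison of post-procedure levels between Visits 1 and 2 survives for patients and families, but needs a paired method. For professionals no VR-versus-SOC comparison is possible on the current schedule.

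This rests on the tick positions being as read and on the schedule taking precedence over the general questionnaire statement. It does not depend on the scale range or on any assumed distribution.

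A reader might also infer that satisfaction must be rated at Visit 3. Such a rating would show whether the first VR impression lasts, but it is a design preference and is not needed to repair this defect.

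**What to change.** - **Endpoint.** Drop the 25% rule for satisfaction. Define the endpoint as the within-person difference in post-procedure satisfaction, Visit 2 minus Visit 1.
- **Method.** Report the mean paired difference with a 95% confidence interval, or use the Wilcoxon signed-rank test if the differences are skewed. Replace the reference to the primary method for this outcome.
- **Raters.** Analyse patients and families separately. The schedule has one combined row, so the CRF should record them as separate entries.
- **Interpretation.** State that SOC always precedes VR, so the difference is confounded with visit order and time.
- **CRF.** List the satisfaction VAS, worded so that it applies equally to SOC and VR visits.
- **Professionals.** Either add a rating at Visit 1 Post or remove the with-and-without-VR claim. If Visit 1 is already complete, only removal remains.
- **Optional.** A patient and family rating at Visit 3 Post.

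The cost is a few lines of SAP text, the CRF entries and, if chosen, one extra professional rating at a visit that takes place anyway. No additional patients or visits are needed.
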